The Effect of Bariatric Surgery on Metabolism,
the Metabolome and the Microbiome in
Patients With Type 2 Diabetes

[figure not shown]
NCT02762708

February 6, 2017

Abbreviations: RYGB: Roux-en-Y Gastric Bypass; CR: Caloric Restriction; CRU: Clinical Research Unit; GLP-1: Glucagon-like peptide-1; DI: Disposition Index; ϕ : β -cell responsiveness; S: Insulin action; EGP: Endogenous Glucose Production; Meal Ra: Meal Appearance; Rd: Glucose Disappearance

The effect of Bariatric Surgery on Metabolism, the Metabolome and the Microbiome in patients with Type 2 Diabetes

Version 3: 2/6/2017

Bariatric surgery is associated with resolution of type 2 diabetes, and remission rates of ~84% have been observed after Roux-en-Y Gastric Bypass (RYGB), influenced by factors such as diabetes duration and treatment [1]. Improvements in glycemic control are seen well before any significant weight loss is produced and patients are often dismissed from the hospital with a marked decrease in their diabetes medications. The necessary calorie restriction that occurs as a result of post-surgical anatomical changes also results in better glycemic control [2]; however this does not explain the known superiority of RYGB over equivalent caloric restriction in improving metabolic parameters, particularly glucose metabolism (Figure 2). Although it is clear that over the

longer-term RYGB may be superior in terms of sustainable effects on fat loss and β -cell function, it remains uncertain to what extent CR contributes to the effect of bariatric surgery on glucose metabolism.

Recently, we have demonstrated that CR and RYGB are both associated with a decrease in fasting endogenous glucose production (EGP) in people with type 2 diabetes (Figure 2). It is unclear if the mechanism by which this is achieved is shared by the two interventions.

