Results of this proposal will be used to support an application for extramural funding at the end of this funding period.

Approach (Figure 1): Volunteers with type 2 diabetes and obesity who are scheduled to undergo RYGB as part of their clinical care will be studied immediately prior to surgery and at 12 weeks post-operatively using a labeled mixed meal to enable simultaneous measurement of glucose metabolism and insulin secretion and

action [10]. Blood samples for targeted metabolic profiling will also be drawn. A fecal sample to characterize the microbiome will be collected at both visits. A matched control group of subjects with type 2 diabetes and obesity who are not scheduled to undergo bariatric surgery will also be recruited and studied at baseline and 12 weeks following caloric restriction similar to that required post-operatively after RYGB. We will utilize weekly meetings with a dietician and a psychologist to ensure compliance with the prescribed diet.

The overall objective of this proposal is to form the basis of a line of investigation that will underpin my research career and future extramural funding. We will address the following specific aims: -

Specific Aim 1: Characterize the changes in the circulating metabolome that occur after Roux-en-Y Gastric Bypass in contrast to caloric restriction alone.

Hypothesis: *Metabolomic changes after Roux-en-Y gastric bypass surgery are associated with a decrease in endogenous glucose production in subjects with type 2 diabetes.*

Specific Aim 2: Characterize the changes in gut microbiome in subjects with type 2 diabetes after Roux-en-Y gastric bypass, in contrast to caloric restriction alone.

Hypothesis: *Gut microbiome changes unique to Roux-en-Y gastric bypass influence remission of type 2 diabetes.*

Preliminary Studies

A. Mathematical modelling of glucose turnover.

The meal minimal model can measure insulin secretion and action [11, 12] [13] and has been validated using hyperglycemic and euglycemic clamps as well as tracer infusions to directly measure glucose turnover. We have shown that insulin sensitivity (S_i) and β -cell responsiveness (ϕ) can be estimated from measured glucose and C-peptide concentrations [12, 14]. The appropriateness of insulin secretion for the prevailing degree of insulin action is assessed by calculating the total disposition index (DI_{total}), which equals the product of insulin secretion and insulin sensitivity ($\phi_{total} \times S_i$).

[figure not shown]

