	Approximately 875kcal daily – 30% protein, 15% fat, 55% carbohydrate		

Table 2: Post-RYGB surgery diet, weeks 0-12.

Study 2: This study will occur in the 12th postoperative (or equivalent) week to ensure that the participants have recovered, have adequate hemoglobin and are tolerating oral intake. The study will be identical to Study 1. The same meal will be consumed in both Study 1 and 2. Subjects will not resume antidiabetic medication in the 12 weeks after surgery. Body composition will be measured the week prior to study. Height and weight will be measured in the CRTU at the time of admission. **Analytic Techniques:** All analytic techniques for blood samples are either established in the applicant's mentor's laboratory or are routinely performed in the Mayo GCRC Mass Spectrometry, Immunochemical Core laboratories or GI imaging and Endoscopy core of the Mayo CTSA.

Exendin-(9,39) Amide Study:

Of the fifteen subjects undergoing Roux-en-Y Gastric Bypass (RYGB), we propose to study four of these subjects in the 4th postoperative week, to ensure that the participants have recovered, have adequate hemoglobin (as determined by PI) and are tolerating oral intake. Subjects will not resume antidiabetic medication in the 4 weeks after surgery. The study will be identical to Study 1 and 2. The same meal will be consumed. Body composition will be measured using dual-energy X-ray absorptiometry (iDXA scanner; GE, Wauwatosa, WI), the week prior to study. Height and weight will be measured in the CRTU at the time of admission. At approximately 0930 (0 minutes) an infusion of exendin-(9,39) amide, an inhibitor of active GLP-1 in humans, will be infused at 300pmol/kg/min in half of the study subjects ([24, 25]. The infusion will be continued till the end of the study, at 360 minutes. The remainder of the subjects will receive a saline infusion. Assignment of exendin-(9,39) amide or saline infusion will be in a randomized fashion (1:1).

Metabolomic analysis: A tandem mass spectrometer with stable isotope dilution for quantification will be used to define the metabolomic profile in both cohorts.

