Microbiome Laboratory. The microbiome lab in the Medical Sciences Building at Mayo Clinic houses 2 computers containing 32-core AMD processors and 64 GB of RAM on which the calculations and modeling proposed will be carried out. The DNA extraction and library preparation facility includes a FastPrep 24 beadbeater, 2 PCR machines, a qPCR machine, a biosafety cabinet, automated and manual gel electrophoresis, and all other equipment and reagents necessary for DNA extraction and 16S rDNA amplification. The Medical Genomics Facility houses 6 Illumina Hi-Seq, 2 Illumina Mi-Seq, Sanger, and Pac-Bio sequencers.

Calculations: Insulin sensitivity (S), β -cell responsivity indices and total disposition index (DI_{total}) will be calculated from plasma glucose and insulin concentrations using the "oral" glucose minimal model [26]. [6-³H] glucose will be used to trace the appearance of the ingested [1-¹³C] glucose and [6,6-²H₂] glucose will be used to trace endogenous glucose production. As previously described, meal appearance will be calculated by multiplying the systemic rate of appearance of [1-¹³C] glucose by the [1-¹³C] glucose in the meal [10]. In addition to measurement of peak hormone concentrations, we will calculate area above basal for the first 2 hours and for all 6 hours after meal ingestion using the trapezoidal rule as previously described [27]. Differences in the metabolomic profile between groups will be quantified. Differences in the microbiome profile between groups will be quantified.

We will subsequently explore correlations between changes in glucose metabolism and multiple metabolites. The metabolome and microbiome analysis will be undertaken in close collaboration with the bioinformatics core ([name], Ph.D.) to examine qualitative and quantitative differences as well as undertake pathway analysis to potentially identify specific pathways affected uniquely by CR or RYGB.

Statistical Analysis. We will examine between-group (RYGB vs. CR) differences from the baseline study to the post-intervention study (Study 2- Study 1). To do so we will utilize an analysis of covariance adjusting for relevant covariates (e.g. age, gender and change in BMI or lean body mass after surgical intervention) as previously described. We will primarily examine between group differences in:

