1. **Endogenous Glucose Production:** Based on data from previous studies [27-29], 15 subjects per group would provide approximately 80% power to detect a 25% difference in nadir EGP values and 87% power to detect a 25% difference in integrated EGP values.
2. **Disposition Index:** 15 subjects per group would provide approximately 80% power to detect an association of intervention type corresponding to a 35% difference in mean DI values relative to the overall mean [28, 30].
3. **Alpha-Aminoadipic Acid:** 15 subjects per group would provide approximately 90% power to detect a 15% difference in mean values.

Interpretation. In the RYGB group, if the improvements in glucose metabolism are associated with a metabolomic signature that is unique, then we will accept our primary hypothesis that metabolomic changes after surgery are associated with a decrease in endogenous glucose production in subjects with type 2 diabetes. We will be able to differentiate between changes in insulin secretion (ϕ_{total}), insulin action (Si) and DI to determine the mechanistic basis for the observed improvements. If the improvements in glucose metabolism are associated with a unique change in the gut microbiome, then we will accept our secondary hypothesis that unique changes in the gut microbiome influence remission of type 2 diabetes. We will specifically be looking for metabolomic markers of the gut microbiome, which have been shown to influence insulin sensitivity [8, 9] and energy harvest, such as short-chain fatty acids [31].

Limitations. Changes in the gut microbiome and circulating metabolome are influenced by dietary intake. Our study design is such that both groups will have similar, but not identical macronutrient composition of their meals. We will minimize differences by utilizing a registered dietician as well as a clinical psychologist to help ensure compliance with the prescribed diet and discourage food consumption outside of what is provided by the study.

Future Directions. Identification of a unique metabolomic profile after RYGB will permit manipulation of concentrations of these substances in overweight subjects with type 2 diabetes to determine their effect on weight loss and glucose metabolism. I hope to use the results of this study to secure extramural funding at the end of this award and be able to continue working on the role of bariatric surgery in the amelioration of type 2 diabetes.

Human Subjects

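### The Interpretation rule turns an association with glucose metabolism into a claim that microbiome change influences diabetes remission, which the plan neither defines nor analyses

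*Combined protocol and SAP*

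**What the plan says.** The Aim 2 hypothesis reads "Gut microbiome changes unique to Roux-en-Y gastric bypass influence remission of type 2 diabetes".

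The Interpretation section turns this into a decision rule. Its condition is that improvements in glucose metabolism are associated with a unique microbiome change. If that is met, "then we will accept our secondary hypothesis that unique changes in the gut microbiome influence remission of type 2 diabetes". The paragraph opens with "In the RYGB group, if the improvements in glucose metabolism are associated with a metabolomic signature that is unique", which introduces the rule for the primary hypothesis. The microbiome sentence does not repeat that scope, although a within-RYGB association is its natural reading.

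The analyses that bear on the rule are these:

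- Calculations: "Differences in the microbiome profile between groups will be quantified". The section adds qualitative, quantitative and pathway analysis with the bioinformatics core, to look for pathways affected by only one intervention.
- Calculations: "We will subsequently explore correlations between changes in glucose metabolism and multiple metabolites".
- Background: 16S sequencing will be used to describe microbial communities, and then how the microbiome acts on circulating metabolites.
- Interpretation: "We will specifically be looking for metabolomic markers of the gut microbiome", with short-chain fatty acids as the example.
- Statistical Analysis: ANCOVA of the change from Study 1 to Study 2, with EGP, disposition index (DI) and alpha-aminoadipic acid as the outcomes primarily examined.

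Outside the hypothesis and the rule, remission appears only in the opening background, as a literature rate of about 84% after RYGB.

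**The concern.** The premise and the conclusion differ in two ways. The outcome changes from glucose metabolism to remission, and the relation changes from association to influence. Nothing in the plan bridges either step. The primary hypothesis, in the same paragraph, is worded as an association, so the causal wording is particular to the microbiome claim.

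If the rule is followed as written, the report will state a causal conclusion about an outcome that the study did not define or analyse. The results are meant to support an application for extramural funding, so the overstatement could be carried into later work.

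**Working it through.** The plan gives no figure to reproduce here. Its power statements cover EGP, DI and alpha-aminoadipic acid; none concerns remission or the microbiome. The check is therefore mainly a reading of the sections against each other.

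**1. Is remission defined or analysed?** No section gives a definition, an assessment time or an analysis.
- HbA1c is listed at the Screening Visit and used for matching; no follow-up HbA1c is stated.
- Under Study 2, "Subjects will not resume antidiabetic medication in the 12 weeks after surgery". Being off drugs in the surgery arm is thus set by the protocol and cannot by itself be an outcome.
- Study Subjects admits people with impaired fasting glucose, so the denominator for remission of type 2 diabetes would also need defining.

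**2. Can the design show influence?** The arms are formed by patient choice: the caloric restriction (CR) group are people not interested in surgery. Fecal samples are taken at two times, around Study 1 and Study 2. The background says that cause or consequence has not been fully investigated. A concurrent association between two changes over one interval cannot settle that.

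**3. Is the premise testable as written?**

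| Link | Stated analysis |
|---|---|
| Microbiome, RYGB v CR | Differences quantified; pathway analysis |
| Microbiome to metabolites | Stated as an intention in the background |
| Metabolites to glucose metabolism | Exploratory correlations |
| Microbiome to glucose metabolism | Presupposed by the rule; no measure, test or criterion |

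**4. What could a direct within-RYGB test detect?** The input from the plan is n = 15. Two-sided alpha of 0.05 and normal data are assumed.
- With 13 degrees of freedom, t = 2.160. Critical |r| = 2.160/√(2.160² + 13) = 0.514.
- By simulation, power at r = 0.65 is about 80%. The Fisher approximation is close: tanh((1.960 + 0.842)/√12) = 0.67.
- With Bonferroni control over an assumed 6 tests (for example two measures by three outcomes), critical |r| is 0.653 and power at r = 0.65 falls to about 53%. Over an assumed 10 tests these are 0.683 and 45%.

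**5. Does weight loss matter?** Suppose that microbiome change and outcome change each correlate ρ with weight loss and have no other link. The correlation induced between them is ρ².

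| Assumed ρ | Induced r = ρ² | Unadjusted test rejects (n = 15) |
|---|---|---|
| 0.7 | 0.49 | about 48% |
| 0.6 | 0.36 | about 27% |
| 0.5 | 0.25 | about 15% |

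After adjustment for weight change, the rejection rate returns to about 5% in each case. The values of ρ are illustrations; the documents give none.

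**The case against.** The strongest defence has four parts.

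*The microbiome plan is fuller than a single sentence.* This stands. A reader might infer that the plan only quantifies group differences. It also includes pathway analysis and a route to glucose metabolism through metabolites, and the rule itself implies that a microbiome-glucose association will be examined. The supportable claim is narrower: no measure, test or criterion is stated for that association.

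*Remission could be assessed.* This stands in part. A reader might infer that the data cannot support any remission measure. But Study 2 repeats Study 1, which includes an overnight fast, and RYGB subjects are then off antidiabetic drugs by protocol. A fasting glucose off drugs could therefore be taken in that arm. The plan does not use it to define remission.

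*The comparison has safeguards.* Also true. The groups are matched on age, gender, BMI, and diabetes duration and severity; the diet is controlled; and the ANCOVA may adjust for change in BMI. These reduce confounding between arms. They do not turn an association into influence.

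*This is a small mechanistic study meant to lead to further work.* That argues for modest wording, whereas the plan speaks of accepting a hypothesis.

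**Conclusion.** Wrong as written. The rule moves from an association with glucose metabolism to influence on remission, and neither step is supported. This rests on the text and needs no numerical assumption.

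The extent is limited to two sentences: the Aim 2 hypothesis and the acceptance sentence under Interpretation. The descriptive part of Aim 2 and the EGP, DI and alpha-aminoadipic acid comparisons are unaffected.

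A reader might go further and argue that a remission analysis would fail anyway, since 84% of 15 leaves only 15 × 0.16 = 2.4 expected non-remitters. The documents do not support that as a finding: the 84% is a background rate given without a definition or time point, and no such analysis is planned. Likewise, the number of microbiome tests is not stated, so the multiplicity figures above are illustrations and do not measure the defect.

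**What to change.** **Specific Aim 2 and Interpretation.** Replace the words about influencing remission with: *are associated with changes in glucose metabolism (integrated EGP, Si and DI)*. Make no claim about remission or causation. In the microbiome sentence under Interpretation, replace accepting the hypothesis with reporting the result as exploratory support for it. Si is included because the Interpretation section itself ties microbiome markers to insulin sensitivity.

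**Calculations.** Add: *Changes in a short pre-named list of microbiome measures will be compared between RYGB and CR by the planned ANCOVA; those that differ will be called unique. Their changes will be correlated with changes in integrated EGP, Si and DI within the RYGB group, unadjusted and adjusted for weight change, with multiplicity control across the list. Any pooled analysis will adjust for arm. All of this is exploratory.*

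**Cost.** Wording in three places, with no new visits or samples. The price is a more modest claim and low power. Only a correlation of about 0.65 is detectable with 80% power in one unadjusted test, and multiplicity control or weight adjustment reduces that further. A null result would therefore say little, and the report should say so.

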- (c) For female subjects: positive pregnancy test at the time of enrollment or study visits
- (d) Previous treatment with thiazolidinediones.
- (e) chronic antibiotic therapy
- (f) active systemic illness
- (g) active microvascular or macrovascular complications of their diabetes.

Potential Risks: Blood sampling. Blood samples are collected by venipuncture for this study. Bruising can occur with venipuncture, as can fainting, etc. Risk Monitoring / Risk Reduction: The samples are collected using aseptic technique in designated venipuncture areas of the CRTU where facilities are available should untoward reactions (fainting, etc.) occur. Given the aseptic nature of the sample collection and the small risk of bruising, the monitoring plan is focused on advising volunteers to call the investigators should they have unusual pain or discomfort from the venipuncture site. Blood drawn within an 12 week period will not exceed 550mL (one pint).

Vascular catheter placement. Catheter insertion, intravenous infusion and blood withdrawal are associated with a small risk of phlebitis. Risk Monitoring / Risk Reduction: This will be minimized by careful attention to sterile technique. If phlebitis occurs, it will be treated conservatively with heat and when appropriate, with antibiotics. The catheters will be cared for by experienced CRTU nurses in order to minimize the risk of these complications. In all protocols, “arterialized – venous” blood will be obtained by placing a hand in which a catheter has been inserted in a heated box during the study. The temperature inside the box is maintained at ~55°C. With prolonged exposure to continuous heat, there is a potential risk of local skin irritation or a minor burn. If this occurs, it will be treated appropriately. Catheter risks will be discussed with the volunteers prior to obtaining consent for the study.

Tracer and Hormone Infusion. Tracers infusions carry a risk of allergic reactions, bruising, discomfort at the site of infusion, and infection. Risk Monitoring / Risk Reduction: All infusates are prepared by trained personnel in a laminar flow cabinet using aseptic technique. Infusions take place on the CRTU where facilities are available should untoward reactions occur. Exendin-(9,39) (CS Bio, Menlo Park CA) will be prepared in a similar manner.

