Radiation. Subjects will be exposed to radiation in this study. Radioactive tracers will be used in the proposed studies. Lean body mass, percent body fat, and visceral adiposity will be measured at the time of screening using DEXA (dual energy x-ray absorptiometry) and CT-scan. Risk Monitoring / Risk Reduction: The lowest dose of radioactive tracers that can be reliably counted in plasma will be used. In all instances, the amount of radiation that a volunteer will receive will be well below levels that result in significant risk of harmful effects. Proposed radiation exposure will be reviewed by the Mayo Clinic Radiation Safety Board prior to initiation of any study. Women who could become pregnant will be required to have a negative pregnancy test prior to participation in each study utilizing radioactive tracers.

Confidentiality. All studies expose participants to the psychosocial risks arising from any breach in confidentiality. The risks include anxiety, confusion, damage to family relationships or a compromised ability to obtain insurance or employment. These risks may not be confined to the individual but may extend to other family members. Risk Monitoring/Risk Reduction: The nature of the information obtained will be explained in detail to each participant. All information will be stored anonymously in the database and only the PI or one of

his designates will have access to the data.

Data Safety and Monitoring Plan. The ultimate goal of this application is to further our understanding the role of different therapies in the management of diabetes. The DSMP utilized will adhere to the protocol approved by the Mayo Clinic IRB. We propose the following plan: -

Data quality and management: The principal investigator will review all data collection forms on an three-monthly basis for completeness and accuracy of the data as well as protocol compliance.

Adverse events grading: The common grading scale listed below will be used to grade AEs:

- 0 No adverse event or within normal limits or not clinical significant
- 1 Mild AE, did not require treatment
- 2 Moderate AE, resolved with treatment
- 3 Severe AE, resulted in inability to carry on normal activities and required professional medical attention
- 4 Life threatening or disabling AE
- 5 Fatal AE

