Attribution scale: An adverse event includes both, an expected side effect that is of a serious nature, or an unexpected side effect/ event regardless of severity. All events will be graded as to their attribution (unrelated to protocol, or possibly, probably, or definitely related to protocol). Any event that is reported to either the principal investigator or his designated research associates by the subject or medical staff caring for the subject and which meets the criteria will be documented as such.

Data Monitoring. The majority of data generated from these protocols will be from analyses performed in our laboratory or the immunochemical core laboratory. Standard quality control procedures are in place for each assay. Genotyping results are examined for consistency between repeated genotypes of a given sample chosen at random. The frequency of data review for this study differs according to the type of data and can be summarized in the following table:

Data type	Frequency of review
Subject accrual (adherence to protocol regarding demographics, inclusion/exclusion)	three-monthly basis
Adverse event/safety rates (injuries)	Weekly
Study data	three-monthly basis
Annual report	Yearly for CRTU, IRB

Informed Consent. Written informed consent will be obtained from all individuals who participate in the study. The principal investigator or member of study team, meet with each participant, review the consent form in detail and confirm the subjects understanding of the study. They answer all questions posed by the participants and when convinced that the subject verbally demonstrates understanding of the protocol obtains a signed consent. Only designated staff are authorized to obtain informed consent.

Benefits: This study exposes subjects to risks detailed above. However, as detailed it will advance our knowledge of how to treat diabetes and help make clinicians make rational therapeutic choices in the future.

VI. Gender/Minority Mix

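### The adverse-event definition and documentation rule, as written, leave out expected non-serious events, so foreseen minor procedural harms may go unrecorded and be undercounted in the weekly safety review

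*Combined protocol and SAP*

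**What the plan says.** Four parts of the combined protocol and SAP bear on this.

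- **Attribution scale (Data Safety and Monitoring Plan).** The definition has two limbs: "An adverse event includes both, an expected side effect that is of a serious nature, or an unexpected side effect", the second at any severity. An event reported to the principal investigator or designated research associates, by the participant or by treating staff, "which meets the criteria will be documented as such". Nothing is said about reported events that do not meet the criteria.
- **Adverse events grading.** "The common grading scale listed below will be used to grade AEs". Grade 1 is "Mild AE, did not require treatment" and grade 2 is "Moderate AE, resolved with treatment". The scale runs from 0 to 5 and does not distinguish expected from unexpected events.
- **Potential Risks (Human Subjects).** This section foresees bruising and fainting with venipuncture, phlebitis with catheters, and allergic reaction, bruising, discomfort and infection with tracer infusions. For the heated hand box it says that "there is a potential risk of local skin irritation or a minor burn". A burn is to be treated, but no recording step is given.
- **Data Monitoring.** The review-frequency table has a row for "Adverse event/safety rates (injuries"), reviewed weekly.

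**The concern.** A weekly review of rates is useful mainly for noticing that a known minor harm is happening more often than it should, for example several hand burns or a run of phlebitis. That needs a complete count of such events. The definition works against it: once a harm has been foreseen, it counts only if it is serious. The minor harms that the plan itself foresees from its procedures are thus the ones with no stated route into the record.

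What is at stake is the completeness of safety monitoring and of any adverse-event rates reported. Staff who follow the definition closely may leave out a minor burn, and staff who follow the grading scale may record it, so recording could also vary between staff. The comparisons of endogenous glucose production, disposition index and alpha-aminoadipic acid do not use adverse-event data and are untouched.

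**Working it through.** There is no figure in the plan to reproduce and no arithmetic to do. The check is a logical one, in three steps.

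**Step 1. Cross expectedness with seriousness and apply the two limbs of the definition.**

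| | Serious | Non-serious |
|---|---|---|
| Expected | Adverse event (first limb) | Neither limb |
| Unexpected | Adverse event (second limb) | Adverse event (second limb) |

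Three of the four cells are covered. The expected, non-serious cell is not.

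**Step 2. Place the foreseen harms.** The plan does not label any event as expected, so I take a harm listed under Potential Risks to be expected. Seriousness is not defined or tied to a grade either, so I take the usual form of bruising, phlebitis managed conservatively, skin irritation, a minor burn or infusion-site discomfort to be non-serious. On those two assumptions all of these fall in the uncovered cell. A severe form of any of them, or a serious allergic reaction or infection, would fall under the first limb and be captured.

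**Step 3. Follow one event, a minor hand burn that is treated and heals.**

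- Potential Risks: foreseen, to be treated, no recording step.
- Definition: expected and non-serious, so neither limb applies.
- Documentation rule: covers events that meet the criteria, so there is no undertaking to document this one, even if the participant reports it.
- Grading scale: by severity it would match grade 2 (grade 1 if untreated), but the scale is for adverse events, which this is not under the definition.
- Weekly review: a burn is an injury and the row names injuries, but no stated step would put this burn into the data reviewed.

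The definition and documentation rule together leave the event out, while the review row suggests that someone expects to see it. The sections do not settle which governs.

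**The case against.** Several points on the other side have force.

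- **The scale and the definition can coexist.** A reader might infer that the plan contradicts itself because its scale grades the very events that its definition omits. The documents do not go that far. The scale applies to adverse events, and grades 1 and 2 are needed for unexpected mild and moderate events. The scale has room for the omitted events; it does not say that they are graded. This stands.
- **The weekly row may already cover burns.** A reader might infer that the review could never see a minor burn. The row refers to safety rates and names injuries, so it can be read to include burns whether or not they meet the definition. This stands, and it limits the conclusion to *may be undercounted*. It does not remove the gap, because no recording step feeds such a reading.
- **The definition may not be exhaustive.** It says that an adverse event *includes* the two categories. That is a possible reading, but the next rule treats them as criteria to be met before an event is documented.
- **Exendin reactions.** A reader might infer that reactions to the exendin-(9,39) infusion would be lost in the same way. The text does not support this. The listed infusion risks are those of tracers, and exendin is mentioned only as being prepared similarly. A reaction specific to exendin is not a listed risk, so it would count as unexpected and be captured at any severity.
- **Other safeguards.** Volunteers are asked to call about unusual pain or discomfort at the venipuncture site, but that covers one procedure, and an expected minor event would still fail the criteria after the call. The monitoring plan also says that it will follow the IRB-approved protocol. Separate institutional procedures might capture minor events, but nothing in these documents shows that they do.
- **Proportionality.** This is a 30-person mechanistic study in which no adverse-event rate is an endpoint. That is a fair reason to rank the point low, but not to leave the wording as it is.

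**Conclusion.** The point holds in a limited form. As written, the definition and documentation rule omit expected non-serious events, and most of the procedural harms foreseen under Potential Risks fall in that category. They may go undocumented and may be undercounted in the weekly review. This is a minor drafting matter for safety monitoring with no bearing on the efficacy analyses.

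The size cannot be put as a number of events. A reader might take the planned study days (30 participants × 2 = 60, plus 4 in the exendin sub-study, giving 64) as the size of the problem. That figure counts exposure to the procedures; without an event rate, which the documents do not give, it says nothing about how many events would be missed.

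The conclusion assumes that a listed risk is an expected one, that these harms in their usual form are non-serious, and that no document outside this one supplies a wider recording rule.

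**What to change.** Reconcile Potential Risks, Adverse events grading, Attribution scale and Data Monitoring with one sentence in the monitoring plan: every untoward event during or after a study procedure is recorded, graded on the existing 0-5 scale and attributed, whether expected or not. Keep the present two-limb wording only as the criterion for expedited reporting. The weekly review of adverse-event and injury rates would then draw on the full record.

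The cost is one changed sentence and slightly more event recording. No treatment, visit, sample or analysis changes.
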